#### 3.2.3 Exploratory Endpoint(s)

The exploratory endpoint for Parts 2 & 3 of the study is:

• Induced sputum concentrations dependent on data availability of voriconazole and N-oxide voriconazole on Day 7 for Part 2 and Days 1, 2 and 3 of each treatment period for Part 3

## 3.3 Study Design

This is an integrated Phase 1, single centre, multi-part, open-label study in both healthy subjects (Part 1), subjects with mild stable asthma (Part 2) and subjects with mild to moderate stable asthma (Part 3).

Part 1 is comprised of 4 separate cohorts containing 6 subjects each. Each subject will receive a single dose of ZP-059 with the dose increasing per cohort following review of safety data from the preceding cohort. The study will have an interleaved design. A further cohort may be enrolled if deemed appropriate to repeat a dose level, assess an interim dose or a dose higher than planned.

Part 2 is comprised of 3 separate cohorts containing 6 subjects each. The treatment period will be for 10 consecutive days with each subject receiving daily doses of ZP-059 (either once daily for 10 days, or twice daily for the first 9 days and once on Day 10), of which the dose and frequency is determined following a safety review of the data from Part 1 Cohort 2. Dose escalation in the next cohort will proceed following completion of the safety assessments 24 hours post dose on Day 10 for a minimum of 4 subjects. A further 2 cohorts may be enrolled if deemed appropriate to repeat a dose level, assess an interim dose, a different dosing regimen or a dose higher than planned.

Part 3 is a two period, randomised crossover study in 16 subjects with a minimum of 6 sputum producers and comprises of 2 cohorts to receive a single dose of ZP-059 in one period, of which the dose is determined following a safety review of the data from Part 1 (Cohorts 1 to 4), and a single dose of 200mg oral voriconazole in the other period. Subjects are randomised to the sequence in which they receive treatment. There will be a minimum wash out period of 96 hours between treatments. Dosing of Part 3 may occur prior to or in parallel with Part 2 of the study.

Further details of the study design can be found in section 4 of the protocol.

## 3.4 Visit Structure

The visit structure and the schedule of activities for each part of the study are detailed in section 1.2 of the protocol. Details of the residential stays, study assessments and procedures at each visit can be found in section 8 of the protocol.

## 4 SAMPLE SIZE

# Part 1 (Single Ascending Dose (SAD) - Healthy subjects) and Part 2 (Multiple Ascending Dose (MAD) – Mild, Stable Asthma Subjects):

This study is not powered for any formal hypothesis test. The sample size of up to 30 subjects (24 subjects plus an additional 6 subjects in 1 optional cohort) in Part 1 and up to 30 subjects (18 subjects plus additional 12 subjects in 2 optional cohorts) in Part 2 was chosen to minimise exposure to Investigational Medicinal Product (IMP) while allowing an adequate assessment of safety at each dose in order to support dose escalation and an adequate number of subjects to assess mean PK parameters. A minimum of 4 evaluable subjects will be required for each cohort for both dose escalation decisions and assessment of mean PK parameters.

#### Part 3 (Mild to Moderate, Stable Asthma Subjects):

This study is not powered for any formal hypothesis test. A sample size of up to 16 subjects was chosen to minimise exposure to IMP while allowing an adequate assessment of safety, PK parameters and drug concentration in sputum. No replacements are foreseen. However, should the drop-out rate for non-safety reasons be high, which may compromise the reliability of the study results, additional subjects could be randomised.

## 5 RANDOMISATION AND BLINDING

Subjects will only be randomised in Part 3 of the study. They will be randomised in a 1:1 fashion to the sequence in which they will receive treatments for the crossover design. There will be no stratification.

As this is an open-label study, no blinding is required.

## 6 INTERIM ANALYSIS

No interim analysis is planned.

Interim safety data reviews will be held to make decisions on the dose escalations during Parts 1 & 2 and the dose of ZP-059 to administer in Parts 2 (starting dose) and 3 of the study. The reviews are conducted by the safety advisory committee (SAC) which is made up of the Principal Investigator ((PI) or delegate) and the sponsor's medical monitor as a minimum. Further details are available in section 6.6 of the protocol.

No outputs will be produced by SQN for these reviews.

## 7 ANALYSIS PLAN

## 7.1 General

Summary statistics for continuous variables will consist of the number of non-missing observations (n), mean, standard deviation (SD), minimum, 25th percentile, median, 75th percentile and maximum, unless specified otherwise. The precision of these variables is defined in the table, figure and listing shells document.

For categorical variables the number and percentage of subjects in each category will be presented, based on the number of non-missing observations apart from the disposition of subjects, protocol deviations, background and demographic characteristics, prior and concomitant medications/procedures and AEs where the percentage will be based on the number of subjects in the analysis set.

The number of missing observations will also be presented for each variable.

## 7.2 General Derivations

This section provides details of general derivations. Derivations specific to the parameter of interest are detailed within the specific SAP section.

#### 7.2.1 Baseline

For Parts 1 & 2 of the study, baseline is defined as the pre-dose value on Day 1. If that is missing it will be defined as the last non-missing value prior to the subject receiving study treatment (pre-dose) on Day 1.

For Part 3 of the study, within-period baseline is defined as the last non-missing value (including scheduled and unscheduled assessments) pre-dose on Day 1 for each of the respective study treatments. Overall baseline is defined as the pre-dose value on Day 1 of Period 1. If that is missing it will be defined as the last non-missing value prior to the subject receiving study treatment (pre-dose) on Day 1.

#### 7.2.2 Study Day

Throughout this SAP any references to "Day XX" refer to the pre-specified visits defined in the protocol (where the study treatment administration visit is Day 1).

Data listings by visit will additionally present study day. Study day will be calculated relative to the first date of administration of study treatment (Study Day 1). For Part 3, the treatment period (Period 1/Period 2) and period day will also be referenced as per section 7.2.3.

#### 7.2.3 Period and Period Day

Period is defined as a subject's treatment window, where Period 1 relates to the treatment period of the first study treatment received by the subject and Period 2 refers to the treatment period of the second study treatment received by the subject.

For the purposes of reporting, data collected from the administration of first study treatment in Period 1 until the day prior to administration of first study treatment in Period 2 will be assigned to Period 1. Data collected on or after the day of the administration of first study treatment in Period 2 will be assigned to Period 2.

Period day will be calculated relative to the first date of administration of study treatment in each period. Data listings by visit will additionally present period and study day where appropriate.

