1.2.3.2 Part 3 Schedule of activities: Day 5 to EDV

				E	nd of 1	reatm	ent Pe	eriod	1 / Tre	eatme	nt Per	iod 2ª						Follow-Up Phone Call ^b	EDV ^d
Study Day						5								(S ^c	7 e	9e	8 to 12 days after last dose	
Treatment Day	TP1 Day 5 /pre dose TP2			TP 2 - Day 1 Day 2 Day 3 Day 5 Times After Dosing (hours)															
							-	Times	After	^r Dosii	ng (ho	urs)							
Study Procedures	96hr / Pre-dose ^j	0																	
Residential Period ^c	←																		
Weight	Х																		
Urine Pregnancy Test f																	Х		X
IMP Administration		Х																	
Physical Examination ^g	Х	-		 				I								—	Х		Х
Safety Labs ^m	Х													Х			Х		Х
Electrocardiogram h	Х			Х			Х		Х					Х			Х		Х
Vital Signs i	Х			Х			Х		Х		Х	Х		Х		Х	Х		Х
Tympanic Body Temperature	х													Х		Х	Х		Х
Pulse Oximetry	Х			Х			Х		Х		Х	Х		Х		Х	Х		Х
Inhaler Device Training	X k																		
Spirometry	Х			Х			Х		Х		Х			Х		Х	Х		Х
Concomitant Medication	4		1						1						•	•			—
Adverse Events	4																		
Blood Samples for PK assessments	Х		Х		Х	Х	Х	Х	Х	Х	Х	Х	Х		Х	Х	Х		Х
Induced Sputum							Х			Х				Х		Х			

Samples for PK										
assessments ¹										

Part 3 Footnotes

- a. Washout interval of a minimum of 96 hours between doses in each treatment period i.e. Day 1 dosing to Day 1 of the next treatment period. **Example of minimum washout period**: Period 1, Day 1 Monday the earliest Period 2, Day 1 of the next treatment period is the following Friday.
- b. Follow-up Phone Call 8 to 12 days after last dose in Period 2, or in the event of early discontinuation to be performed after last dose in Period 1.
- c. Discharge from clinic after completion of treatment period 2, 24-hour post-dose assessments.
- d. The EDV is only to be performed for subjects who discontinue during a treatment period (prior to Study Day 5 or Study Day 9) i.e. is not required if discontinue during the washout period.
- e. Subjects will return on Day 7 and Day 9 for collection of PK blood sample, induced sputum sample (Day 7 only) and safety evaluations.
- f. All female subjects.
- g. Full physical examination at screening, Study Day 5 and Study Day 9. Symptom directed examination; if required at any other visits or times at the discretion of the investigator.
- h. Performed in triplicate. For assessment of time windows, the time of the first ECG of the triplicate will be used.
- i. Systolic and diastolic blood pressure, pulse rate and respiratory rate.

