- j. All +96-hour procedures for Treatment Period 1 are to be performed prior to Treatment Period 2 dosing and can also be considered as Treatment Period 2 pre dose assessments.
- k. Of the relevant treatment period only, training will be performed pre-dose on Day 1.
- I. A minimum of 6 out of the 16 subjects to be randomised in Part 3 must provide a sufficient sputum sample at screening as per inclusion criteria 13.
- m. Clinical safety laboratory samples (clinical chemistry, haematology and urinalysis), Samples for clinical chemistry will be obtained following a fast of at least 8 hours (water permitted).

2. Introduction

Asthma is a chronic condition which occurs as a result of immune response in the bronchial airways, causing intermittent inflammation and airway swelling. Many factors, including infection as well as different allergens can irritate and inflame the airways, leading to worsening of asthma symptoms.

The frequency of *Aspergillus* sensitisation in asthmatic subjects varies, with a range from 16% to 38% being reported in different geographical regions [1]. Some asthmatics with sensitisation to *Aspergillus* present with allergic bronchopulmonary aspergillosis (ABPA), a progressive fungal allergic lung disease, which can be a cause of poorly controlled asthma. While ABPA is often under-diagnosed due to the complexity and relative lack of standardisation of diagnostic criteria, prevalence of ABPA in asthmatics of up to 12.9% has been reported [2, 3].

The link between asthma severity and fungal allergy is well established. Indeed, sensitisation to fungal allergens and ABPA are associated with the risk of severe asthma exacerbations requiring multiple hospital and intensive care admission [4, 5] and management with prolonged courses of systemic corticosteroids and azoles [6], which are associated with significant adverse effects.

In this setting, there is a need for development of new, effective and well tolerated therapies to control fungus-associated inflammation of the airways. Inhaled administration of antifungals like voriconazole could potentially be an effective alternative treatment option for ABPA and may improve asthma control and reduce its severity and frequency of exacerbations.

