#### 7.5.2 Part 3 Specific Presentations

Safety and PK data will be summarised by treatment group and all other data will be summarised in tabular form by treatment sequence and overall.

Listings will be sorted by treatment or treatment sequence as appropriate, screening number and date/time of assessment.

Treatment groups will be presented in the following order using these labels:

- ZP-059
- Oral Voriconazole

Treatment sequences will be presented in the following order using these labels:

- ZP-059 / Oral Voriconazole
- Oral Voriconazole / ZP-059

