#### 7.5.3 General Presentations

Graphical presentations of the data will also be provided where appropriate.

Only scheduled post-baseline assessments will be tabulated; post-baseline repeat/unscheduled assessments will not be tabulated, although they will be listed.

Eligibility, screen failures and analysis sets will be summarised using the Screened set. Background and demographic characteristics, study completion/withdrawal, and protocol deviations will be summarised using the Enrolled Set. Prior/concomitant medications, administration of study treatment and exposure and safety will be summarised using the SAF.

All other data will be summarised using the SAF apart from PK, which will be summarised using the relevant PK sets.

Eligibility and screen failures will be listed using the Screened set. Completion/withdrawal and analysis set listings will be based on the Enrolled set. PK listings will be based on the PK sets. Safety listings will be based on the SAF set. All other listings will be based on the Enrolled set.

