## 7.9 **Prior and Concomitant Medications**

Medications will be coded using the latest World Health Organization Drug dictionary (WHO Drug) version. The version used will be indicated in the data summaries and listings.

Prior medications are defined as those taken within 28 days prior to screening. Medications that are ongoing at screening or started after screening will be deemed to be concomitant medications. If medication dates are incomplete and it is not clear whether the medication was concomitant, it will be assumed to be concomitant.

For Part 3, the following rules will be used to define whether a medication is concomitant and which treatment they should be assigned to:

- Concomitant to Period 1 only is defined as medication administered from first administration of study drug for Period 1 and finishing prior to the first administration of study drug for Period 2.
- Concomitant to Period 2 only is defined as starting from first administration of study drug in Period 2.
- A treatment starting before the end of Period 1 and continuing into Period 2 will be reported under both periods.
- If medication dates are incomplete and it is not clear whether the medication was concomitant to a single treatment period, it will be assumed to be concomitant to both periods

The number and percentage of subjects taking concomitant medications will be summarised by medication class and standardised medication name, where medication class and standardised medication name will be presented alphabetically. In summary tables, subjects taking multiple medications in the same medication class or having the same standardised medication recorded multiple times in the study will be counted only once for that specific medication class and standardised medication name.

Prior and concomitant medication data will be listed and flagged accordingly.

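### The SAP's calendar-day period cut moves the Part 3 Period 1 +96 h safety assessments into Period 2

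*SAP*

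**What the plan says.** SAP 7.2.3 sets the reporting periods for Part 3. Period 1 runs from the first dose to the day before the Period 2 dose, and then: "Data collected on or after the day of the administration of first study treatment in Period 2 will be assigned to Period 2". It makes no exception for pre-dose records on that day and does not provide for a record to count in both periods.

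The protocol's Part 3 schedule (1.2.3.2) has one combined column on Study Day 5, headed "TP1 Day 5 /pre dose TP2". It is marked for safety labs, ECG, vital signs, pulse oximetry and spirometry, and also for temperature, physical examination and PK blood. Footnote j says "All +96-hour procedures for Treatment Period 1 are to be performed prior to Treatment Period 2 dosing" and adds that they "can also be considered as Treatment Period 2 pre dose assessments".

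Four other SAP rules bear on the result:

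- **Baseline (7.2.1):** the within-period baseline is the last non-missing value "pre-dose on Day 1 for each of the respective study treatments".
- **Part 3 tables (7.5.2):** "Safety and PK data will be summarised by treatment group".
- **Visits shown (7.5.3):** "Only scheduled post-baseline assessments will be tabulated".
- **Other data types:** concomitant medications belong to Period 1 only when "finishing prior to the first administration of study drug for Period 2" (7.9). AEs are likewise split at the Period 2 administration (7.13.1.1).

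**The concern.** The protocol intends the Study Day 5 pre-dose assessments to close Period 1 and to open Period 2. The SAP's period rule keeps only the second role. Because tables are by treatment and treatment follows from period, the values a subject shows 96 h after the Period 1 treatment would not be tabulated under that treatment. They would serve only as the starting point for the other one.

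The SAP also disagrees with itself. An AE that starts on Study Day 5 before dosing is credited to the Period 1 treatment, while a laboratory value recorded at the same visit is filed under Period 2.

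Safety and tolerability is the primary endpoint in each part (SAP 3.2.1), and the by-visit summaries are how it is reported. For labs and ECG, the +96 h record is the only scheduled Period 1 assessment after the one about 24 h post-dose. A change that the investigator does not judge clinically significant would be absent from the 96 h row of the treatment it followed. It would also shift the baseline against which the second treatment is measured.

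**Working it through.** The documents give no figure of their own on this point. The check applies the stated rule to the planned schedule and counts subjects.

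**Inputs**

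- Dose-to-dose interval: at least 96 h (protocol 4.1.3; SAP 3.3).
- Residence to Day 6, with discharge after the Period 2 24 h assessments (protocol 4.1.3). This places the Period 2 dose on Study Day 5.
- Period 1 +96 h procedures: before the Period 2 dose (protocol 1.2.3.2, footnote j).
- Period 2 96 h visit: Study Day 9 (protocol 4.1.3).
- 16 subjects (SAP 3.3), randomised 1:1 to sequence without stratification (SAP 5). Assumed here: exactly 8 per sequence, no dropout, no missing visits.

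**Step 1: where the Period 1 +96 h record goes.** The record is taken to be collected half an hour before the 96 h mark.

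| Dose-to-dose interval | Period 2 dose on | Calendar-day rule (SAP 7.2.3) | Cut at Period 2 dose time |
|---|---|---|---|
| 96 h (as scheduled) | Study Day 5 | Period 2 | Period 1 |
| 120 h | Study Day 6 | Period 1 | Period 1 |

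The misassignment occurs when the Period 2 dose falls on the same calendar day as the +96 h visit. That is the scheduled case.

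**Step 2: subjects in each treatment's 96 h row.**

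- Calendar-day rule: only the Study Day 9 record counts as a 96 h value. ZP-059 has the 8 subjects who received it in Period 2, and oral voriconazole has the other 8. Subjects with a 96 h value under both treatments: 0.
- Dose-time rule with dual use: ZP-059 8 + 8 = 16; oral voriconazole 8 + 8 = 16; subjects under both: 16.

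At equal SD, the standard error of a 96 h mean is larger by √(16/8) = 1.41 under the calendar-day rule.

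**Step 3: what Period 1 data remain.** In the schedule for screening to Day 4 (protocol 1.2.3.1), the last Period 1 values before Study Day 5 are at about 24 h for labs and ECG, and at 48 h for vital signs, oximetry and spirometry.

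**Step 4: illustration.** Suppose a proportion p of subjects show some given shift at 96 h. The chance that at least one appears in a treatment's row is 1 − (1 − p)^n. The documents give no value of p, so the rates below are assumptions.

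| p | n = 16 | n = 8 |
|---|---|---|
| 5% | 1 − 0.95^16 = 56.0% | 1 − 0.95^8 = 33.7% |
| 10% | 1 − 0.90^16 = 81.5% | 1 − 0.90^8 = 57.0% |
| 20% | 1 − 0.80^16 = 97.2% | 1 − 0.80^8 = 83.2% |

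These are chances of display in one table row, not of detection anywhere in the report.

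**Step 5: PK.** The Period 1 96 h blood sample is taken at the same visit. SAP 3.2.2 and 7.12.3 take AUC0-t to 96 h in Part 3, so the SAP evidently expects that sample in the Period 1 profile. The wording of 7.2.3 does not say so.

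**The case against.** The strongest reply is that by-visit tables may be built on protocol visits and not on the 7.2.3 label. SAP 7.2.2 ties day labels to the protocol's visits, SAP 3.4 takes the visit structure from protocol 1.2 (which contains footnote j), and the table shells are a separate document that could map this visit to Period 1 96 h. That is possible. But 7.2.3 says its rule applies for reporting purposes, 7.2.2 only defines labels, and a Part 3 table by treatment needs a period to assign the treatment. Shells that placed the record in Period 1 would contradict 7.2.3, and the text would still need correcting.

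A second reply is that footnote j is permissive, and that the calendar-day rule keeps the Period 2 pre-dose value in Period 2, where the within-period baseline needs it. A bare dose-time cut would move it out. This is correct, and it is why the fix must state dual use as well as change the cut. The AE and medication rules are specific to those data and would govern them in any case.

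A third reply concerns impact, and much of it stands. No formal safety analysis or hypothesis test is planned, so no planned estimate uses a within-subject 96 h contrast. Labs, vital signs, spirometry and ECG are listed with change from baseline and out-of-range flags. Clinically significant abnormalities become AEs and are attributed by dose time. An interval long enough to move the Period 2 dose to a later day would avoid the problem. These points limit the consequence; they do not make the rule right for the planned schedule.

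**Conclusion.** The concern holds. As written, SAP 7.2.3 assigns the Period 1 +96 h safety assessments to Period 2 for every subject dosed on the planned schedule. That removes one of the two roles the protocol gives them and is inconsistent with the dose-time cuts in SAP 7.9 and 7.13.1.1. Each treatment's 96 h row falls from 16 subjects to 8, and the two rows then describe different subjects.

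These counts assume 16 completers, 8 per sequence, Period 2 dosing on Study Day 5, and tables that follow the period rule literally. No source data are lost, AE and concomitant medication attribution is unaffected, and no PK loss is claimed. The damage is confined to by-treatment summaries, but these report the primary endpoint. It should be corrected before the tables are produced.

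**What to change.** Make three changes to the SAP text:

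1. **Period boundary (7.2.3).** Data from the Period 1 dose up to the time of the Period 2 dose belong to Period 1; data from the time of the Period 2 dose onward belong to Period 2.
2. **Dual use.** Study Day 5 pre-dose records count both as Period 1 96 h values and as the Period 2 within-period baseline, with a reference to protocol 1.2.3.2, footnote j.
3. **PK.** The Period 1 serum profile includes the 96 h sample.

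The cost is three sentences and one visit-mapping line in the programming. Data collection does not change. The table shells should be checked against the new wording.
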